may become an issue. In this light, multiple casts changes become necessary to reduce the risk of soft tissue complications and to provide patient comfort. This increases the wastage of materials for the fibreglass casting as well as increases healthcare burden for the cast changes.

Castomize has created a 4D printed cast with its proprietary materials and designs aimed at overcoming the challenges in the traditional casting methods. Its 4D printed casts are lightweight and breathable, allowing contact with water and hygiene. Its design facilitates visualisation of the skin and soft tissue conditions. It is also remouldable, potentially only requiring one device for the duration of the patients care journey.

The design of the 4D printed cast was done in collaboration with orthopaedic clinicians, prosthetists and senior casting technicians optimised for clinical use. A biomechanical test was performed to evaluate the biomechanical properties of the 4D printed cast in comparison to the conventional fibreglass casts and were found to be less stiff and with a lower load to failure. This was however accessed to be not clinically significant.

Therefore, this study aims to compares the Castomize 4D printed casts versus the conventional fiberglass cast in fracture immobilisation and various patient reported outcomes.

Methods/design

This manuscript is written according to the Consolidated Standards for Reporting Trials (CONSORT statement) and Standard Protocol Items: Recommendations for Interventional Trials (SPIRIT guidelines).

Objectives

The primary aim of the study is to assess non inferiority of the Castomize 4D printed cast versus conventional fibreglass casts in fracture immobilisation and reduction.

The secondary aim of the study is to assess differences in patient reported outcomes measures (ARCEQ, comfort of the cast, EQ-5D-5L, cost-effectiveness and adverse events occurrence) in the Castomize 4D printed cast versus conventional fibreglass casts.

Design, participants, interventions and outcomes

Study design and randomization

A randomised controlled trial will be conducted in a single institution: TTSRH.

Patients will be recruited at the outpatient clinic. Patients who meet the inclusion and exclusion criteria will be recruited and randomised into 2 groups. Randomisation will be carried out via block randomisation via a computer generated randomization sequence.

Group 1: Castomize 4D printed cast (Figure 2)

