Patients randomized to group 1 will undergo fracture immobilisation with the Castomize 4D printed cast via the care team (Casting technician/ clinical team). The Castomize 4D printed cast is appropriately heated and then moulded to the patients wrist as per usual manipulation and reduction techniques. The cast is held in position until hardened.

Group 2: Conventional casting (Figure 1)

Patients randomized to group 2 undergo fibreglass casting as per the standard of care.

In both groups, post casting X-rays are taken to assure fracture reduction and recasting may be attempted in the event of inadequate fracture reduction.

A patient information sheet will be provided to the patient explaining the study protocol, and what to look out for in caring for their casts.

Inclusion criteria

- Age \geq 21 years
- Distal radius fracture for conservative treatment within 3 weeks of initial injury

Exclusion criteria

- Concomitant injuries to the ipsilateral extremity, interfering with the treatment of the DRF (Example: concomitant elbow fracture that requires further immobilisation with a above elbow cast)
- Inability to complete study forms due to any cognitive, mental issues.
- Pregnant women

Study procedures and timeline

Measurements will take place at 6 time points as shown in Table 1. These time points are baseline (T0), 1 week (T1), 2 weeks (T2), 6 weeks (T3), 3 months (T4) and 6 months (T5) after inclusion in the study. At T0, baseline characteristics will be gathered. An inclusion form will be filled in by the treating physician providing fracture and treatment-specific information. Second, patients receive a questionnaire, providing predominantly patient and injury-specific information. The list of baseline characteristics is shown in Table 2. Patients receive questionnaires at T1 to T5. These questionnaires are carried out by phone call. Posterior-anterior (PA) and lateral radiographs of the wrist will be taken at T0 (before and after reduction) and during follow-up at T1 –T4 as per standard of care. Physical examination of the wrist will take place at T4 and will be performed by the research team. Study visit may be administered via phone call. Functional tests will be performed at patient earliest appointment.

Table 1 Schedule of activities

	T0 Baseline	T1 D7 \pm 3	T2 D14 \pm 3	T3 D35 \pm 7	T4 D84 \pm 14	T5 D168 \pm 21
Inclusion form	✓					
X-rays*	✓	✓	✓	✓	✓	
Functional tests**					✓	✓
VAS		✓	✓	✓	✓	✓
Photograph		✓				
Comfort of cast		✓	✓	✓		

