Analgesic use		✓	✓	✓	✓	✓
EQ 5D5L		✓***		✓	✓	✓
ARCEQ				✓	✓	✓
MCQ- iMTA				✓	✓	✓

PCQ- iMTA				✓	✓	✓
-----------	--	--	--	---	---	---

*X-rays before and after reduction (obtained from standard of care results if available)

**ROM, grip strength done by study team. ROM, DRUJ and Kapandji will be collected as part of standard of care if available

*** EQ 5D5L status pre-fracture and post-fracture sustainment

Table 2 Baseline characteristics

Baseline characteristics	
Date of emergency room visit	Sex
Affected wrist	Date of Birth
Method of reduction	
	Hand dominance
	Mechanisms of injury
	Smoking Status
	General medical history
	Previous injuries of the affected extremity
	La Fontaine criteria

Outcome

Primary outcome The primary outcome of this study is the occurrence of fracture displacement assessed on PA and lateral radiographs at 1, 2 and 6 weeks. Displacement of the radius is defined by: As compared to the post reduction radiograph at T0, Displacement of : > 15° of dorsal angulation, > 20° of volar angulation, < 15° of radial inclination, > 3mm of radial shortening and > 2mm intraarticular step-off or gap. Measurements will be on standard PA and lateral radiographs of the wrist by trained members of the research team.

Secondary outcomes An overview of measurements is shown in Table 1.

- Comfort of the cast assessed via pictorial representation of pressure marks or areas of discomfort.
- Severity of pain evaluated with the Visual analogue Score (VAS)
- Patient will describe their average wrist symptoms over the past week on a scale of 0-10 using Adult Rated Cast Evaluation Questionnaire (ARCEQ) [6][7].
- Quality of life will be assessed using the 5-level EuroQol (EQ-5D-5L) scoring questionnaire.
- Cost-effectiveness will be measured using the Medical Consumption Questionnaire (iMCQ) and the Production Consumption Questionnaire (iPCQ) [8].
- Physical examination:
 - Range of motion (ROM) of the wrist will be measured with a goniometer. ROM concerns dorsal flexion, volar flexion, radial deviation, ulnar deviation, pronation and supination.
 - Grip strength will be measured with a Jamar hydraulic hand dynamometer. The maximum score for each side over 3 attempts will be used
 - Specific testing of the wrist and hand will be performed namely:
 - distal radioulnar joint (DRUJ) stability tested with the DRUJ ballottement test

- opposition of the thumb using the Kapandji score

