- finger stiffness will be measured with finger-to-palm distance, tested from the tip of the finger to the distal palmar crease when the fingers are in maximal active flexion

ROM and grip strength on the injured side will be compared with the uninjured side.

- Number of conversions to surgical treatment and other (serious) adverse events will be monitored. (Eg: Skin complications)

It is expected that a proportion of patients will fail conservative treatment with displacement of the distal radius fracture at week 1 or week 2 follow up. These patients will continue with surgical fixation of their fractures and no further trial procedures will be required.

Adverse events reporting

All adverse events reported by the patient or observed by the treating physician or researcher will be recorded. Serious adverse events (SAE) will be reported to the Domain Specific Review Board (DSRB), which approved the protocol.

Serious adverse events are defined as:

- Skin related problems requiring surgical intervention (Eg: Ulcer, infection, necrosis)
- Compartment syndrome
 - Cast related injury to the patient resulting in loss of limb or life

Study related serious adverse events are defined as:

- Compartment syndrome

Fig 1 Conventional Fiberglass cast[9]

Fig 2 CASTomize 4D printed cast

Data analysis

General descriptive statistics will be performed on baseline patient and fracture characteristics. Patients will be analysed according to the intention-to-treat principle.

Primary outcome

The primary outcome, fracture re-displacement, will be analysed using a mixed-effects logistic regression. To account for clustering, a random intercept for the hospitals will be used. Fixed effects will be the covariates we adjust for as reported in the literature, namely age, presence of osteoporosis, and fracture characteristics. If new prognostic factors will be identified and reported in the literature, these factors will also be added as covariates.

Secondary outcomes

For secondary outcomes, trends between baseline and follow-up time points (T0-T5) will be assessed using linear mixed models for repeated measures. This accounts for comfort of the cast, recovery of function and grip strength, pain severity (VAS), ARCEQ and EQ-5D-5L scores. The number of conversions to surgical fixation and complications will be determined using Fisher Exact or Chi-square test, depending on the magnitude of results.

Cost-effectiveness analysis

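### The primary model has a hospital random intercept in a one-hospital trial, and its covariate list is incompletely defined and open-ended with 30 patients

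*Combined protocol and SAP*

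**What the plan says.** All references are to the combined protocol and SAP.

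- **Data analysis, Primary outcome.** Re-displacement is to be analysed by mixed-effects logistic regression. The only random effect is for hospital: "To account for clustering, a random intercept for the hospitals will be used". On covariates: "Fixed effects will be the covariates we adjust for as reported in the literature, namely age, presence of osteoporosis, and fracture characteristics". The next sentence reads: "If new prognostic factors will be identified and reported in the literature, these factors will also be added as covariates".
- **Study design and randomization.** "A randomised controlled trial will be conducted in a single institution: TTSRH". The units randomised are recruited patients, in two groups: "Randomisation will be carried out via block randomisation via a computer generated randomization sequence".
- **Objectives.** "The primary aim of the study is to assess non inferiority of the Castomize 4D printed cast". No margin is given anywhere.
- **Outcome.** "The primary outcome of this study is the occurrence of fracture displacement assessed on PA and lateral radiographs at 1, 2 and 6 weeks".
- **Study procedures and timeline, and Table 2.** Fracture data are collected: "An inclusion form will be filled in by the treating physician providing fracture and treatment-specific information", and Table 2 lists the La Fontaine criteria. Osteoporosis has no named item in Table 2, though general medical history could capture it.
- **Abstract.** The sample is 30 patients in total.

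**The concern.** There are two defects of unequal weight.

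The hospital intercept does not fit the design. There is one hospital, so there is no between-hospital variation to model. This is a wording repair.

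The covariate list matters more. Nothing says which fracture items enter the model, how many, or how they are coded, so two analysts following the text could fit different primary models. The instruction to add newly reported factors has no cut-off date, cap or selection rule, so the model could grow after outcomes are known. With 30 patients, each extra coefficient makes it more likely that the treatment odds ratio has no finite estimate, and widens its interval when it has one.

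**Working it through.** **1. The hospital term.** With one cluster, the marginal likelihood at random-intercept SD *s* is the ordinary logistic likelihood averaged over a normal distribution of intercepts. An average cannot exceed the maximum, and the maximum is reached at *s* = 0. As an illustration, take 9 of 30 displaced and the fixed intercept at log(9/21). The log-likelihood is −18.33 at *s* = 0, −18.80 at 0.5, −19.31 at 1 and −19.97 at 2. The variance estimate goes to zero and ordinary logistic regression remains. This step needs no assumption about event rates.

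**2. Coefficients and events.** Arm, age and osteoporosis make three coefficients. One to three fracture factors bring the total to 4–6, and two factors added later bring it to 8. The documents give no displacement rate, so 20/30/40% is assumed, giving 30 × 0.20 = 6, 30 × 0.30 = 9 and 30 × 0.40 = 12 events. Events per coefficient run from 6/6 = 1 to 12/4 = 3 with 4–6 coefficients, and from 6/8 = 0.75 to 12/8 = 1.5 with eight.

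**3. Arm alone, exact.** Allocation is assumed 1:1, 15 per arm. The treatment coefficient has no finite estimate when either arm has none or all of its patients displaced: 1 − (1 − (1−p)^15 − p^15)². At p = 0.20, 0.8^15 = 0.0352 and the result is 6.9%. At 0.30 it is 0.9% and at 0.40 it is 0.1%.

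**4. More coefficients, simulated.** There were 4,000 trials per risk, with no true treatment effect. Assumed log-odds were 0.5 per SD of age, 0.7 for osteoporosis (30% prevalence) and 0.6 for each of three binary fracture factors (40%); the two later factors (40%) had no effect. Separation of the treatment coefficient was found by linear programming. The limit ratio is the upper over the lower 95% limit of the treatment odds ratio, exp(2 × 1.96 × SE), as a median over trials with a finite estimate.

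| Model, ordinary logistic | No finite treatment estimate, % (risk 20/30/40%) | Limit ratio (risk 20/30/40%) |
|---|---|---|
| Arm alone | 6.9 / 0.9 / 0.1 | 43 / 26 / 20 |
| 4 coefficients | 9.2 / 2.1 / 0.5 | 84 / 48 / 36 |
| 6 coefficients | 19.3 / 5.8 / 2.3 | 159 / 87 / 61 |
| 8 coefficients | 36.3 / 15.6 / 7.6 | 339 / 164 / 106 |

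A repeat with 500 runs per risk gave 9.8/1.6/0.4, 18.4/4.8/2.0 and 36.0/14.0/8.6% for 4, 6 and 8 coefficients.

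**5. What improves matters.**

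| Model | No finite treatment estimate, % | Limit ratio |
|---|---|---|
| Arm, age, fracture count; ordinary logistic | 7.5 / 1.4 / 0.2 | 76 / 42 / 31 |
| Same list; Firth | none | 54 / 34 / 28 |
| Same list plus osteoporosis; Firth (1,500 runs per risk) | none | 62 / 40 / 32 |

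Against four coefficients fitted by ordinary logistic regression, the short list with Firth lowers the ratio by 84 − 54 = 30, 48 − 34 = 14 and 36 − 28 = 8. Penalisation accounts for 76 − 54 = 22, 42 − 34 = 8 and 31 − 28 = 3 of this: most of it at 20% and 30% risk, less than half at 40%. The Firth ratios cover every trial, including those where the ordinary fit has no finite estimate.

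For Firth with arm, age and fracture count (8,000 runs per risk and effect), the profile 95% upper limit fell below the true odds ratio in 2.1% of trials with no effect, and in 2.6/2.4/2.5% with a true odds ratio of 3. Nominal is 2.5%. Wald limits were conservative (0.5–1.8%).

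**The case against.** The strongest reply is that this is a 30-patient pilot and the sample size dominates. Arm alone already gives a limit ratio of 43/26/20. On the smallest reading of the text, the excess of non-finite estimates over arm alone is only 9.2 − 6.9 = 2.3, 2.1 − 0.9 = 1.2 and 0.5 − 0.1 = 0.4 percentage points. The 36% figure needs a 20% risk, three separate fracture factors and two later additions, and the documents do not say that any of these will occur. All of that stands, and it limits the size of the point. It does not rescue a list that is neither defined nor closed: that defect is in the text and needs no assumed rate.

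Three stronger readings are tempting and are not supported.

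- *The hospital intercept biases the result.* It does not; it drops out.
- *The model omits the treatment arm, or counts three radiographs per patient as independent.* Arm is not named as a fixed effect, but a comparison of two casts implies it. The outcome is the occurrence of displacement, and patients who displace at week 1 or 2 go on to surgery with no further trial procedures. One result per patient is therefore the natural reading. Both deserve a clarifying phrase; neither is an error.
- *Osteoporosis must go, or at most two covariates can be kept.* Firth regression with osteoporosis retained converged in every run, with only a modestly wider interval. The sponsor named it as prognostic, and dropping it would be a preference.

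**Conclusion.** The point holds and should be fixed. The hospital random intercept contradicts the single-institution design but is harmless. The undefined fracture variables and the open-ended addition of covariates are the substantive fault, because they leave the primary model unfixed and following the rule makes the treatment estimate less stable. The sizes rest on assumed displacement risks, covariate prevalences and effects, and 1:1 allocation; the contradiction and the open list do not.

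A reader might infer that the covariate rule decides whether non-inferiority can be shown. The documents do not support that. No margin is stated, so there is no value to hold the confidence limit against, and most of the imprecision would remain under any covariate rule.

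**What to change.** 1. Delete the hospital random intercept.
2. Delete the sentence that adds newly reported factors, or confine such factors to a labelled exploratory analysis.
3. Specify a Firth penalised logistic regression with one result per patient (any displacement through the T3 radiograph) and treatment arm as the effect of interest. Give a short closed covariate list with coding fixed before any outcome data are seen. An example is age (continuous), osteoporosis if it is recorded, and one fracture-severity variable built from the La Fontaine criteria already collected. Report the odds ratio with a profile penalised-likelihood 95% CI.
4. Optionally, report an unadjusted risk difference with a Newcombe 95% CI alongside. By exact enumeration its mean half-width is 27.8/29.7/30.8 percentage points at 20/30/40% risk, with coverage 95.0/94.5/95.1%. State in advance which estimate is primary.

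The cost is analysis wording only, provided that osteoporosis is either already recorded or left out. The downside is that separate fracture factors are not adjusted for individually and the interval stays wide. Three separate matters remain open: the non-inferiority margin, the timing of T3 (6 weeks in the text, day 35 ± 7 in Table 1), and how a patient with a missing radiograph is classed.

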CASTomize Pilot Study Protocol

Principle investigator: [name]

Co-investigator: [name], [name]

Industrial collaborator: [name], [name], [name]

CASTomize pilot study protocol: a randomized controlled trial comparing CASTomize 4D printed cast versus standard of care fiberglass cast on fracture reduction and patient reported outcomes.

Abstract

Background: For many years, traditional fibreglass casting has been the gold standard of immobilisation for distal radius fractures (DRFs). However, the traditional method of casting has obvious disadvantages such as poor patient comfort, inability to be in contact with water, difficulty observing skin underneath and requiring multiple cast changes in the patients care journey. This study compares the Castomize 4D printed casts versus the conventional fiberglass cast in fracture immobilisation, and various patient reported outcomes.

Methods/design: This study is a randomised control trial comparing Castomize 4D printed cast versus conventional fibreglass casts in isolated conservatively treated distal radius fractures. The primary outcome measure is fracture reduction. Secondary outcome measures include patient reported outcome measures such as the Adult Rated Cast Evaluation Questionnaire (ARCEQ)[1][2], comfort of the cast, quality of life assessed with the EQ-5D-5L questionnaire[3], cost-effectiveness and adverse events occurrence. In total, 30 patients will be included and followed for 6 months.

Trial registration: Pending

Registration number: Pending

Background

Displaced distal radius fractures (DRF) are very common in the adult population and their incidence is still on rising trend due to aging population. This is an issue which is pervasive across all ages, but most common in the elderly. In 2019, 180 million fractures happened worldwide. An average of 5 fracture incidents occurs every second. The current gold standard in fracture immobilisation is via the application of a fibreglass cast. However, the current fibreglass cast has multiple disadvantages. The cast is bulky, has poor ventilation and cannot come into contact with water. This gives patients considerable discomfort, and are unable to bathe and provide hygiene to their injured limb for the duration of the casting. Because the cast is not breathable, skin maceration, itchiness and wounds

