Both cost-effectiveness (CEA) and cost-utility (CUA) analysis will be performed from a societal perspective. For the calculation of medical costs, we will use charges as published in Singapore guidelines as a proxy of real costs. The unit per price of the cast application in patients with DRF will be calculated with the microcosting method. Intramural costs (i.a. additional diagnostics, number of hospital visits, in case of hospital admission the length of stay etc.) are collected from the electronic health record. Productivity costs will be registered in detail by the iPCQ. The iMCQ and the iPCQ are validated by the Institute of Medical Technology Assessment (Erasmus University, Rotterdam, The Netherlands).

The difference in costs and effects of CASTomize instead of a circumferential cast will be calculated as incremental cost-effectiveness ratio (ICER). The primary effect outcome measures will be the number of re-displacements for the CEA and quality-adjusted life years (QALY) for the CUA. QALYs will be measured, based on the Singaporean tariff for the EQ-5D-5L.

The sensitivity analysis will assess the robustness of the results to changes in costs and effect parameters. Bootstrapping with 1000 replications will be used to estimate 95% confidence intervals around cost differences and the uncertainty surrounding the ICERs. This will be graphically presented on cost-effectiveness planes and acceptability curves using the net benefit framework. For the time horizon of 6 months, discounting is not necessary.

Data management

All data are handled confidentially and anonymized in compliance with the Singapore Personal Data Protection Act (PDPA). Personal data of participants will be changed by a study number. This number is used for all study documentation, study reports and publications. The key of this study number will be handled by an independent researcher. During the study period, all data will be collected and managed using GemsTracker electronic data capture tools. Paper case report forms are entered in GemsTracker by the researcher and the original paper case forms will be filed in the investigator site file at the recruiting hospital. All data is stored for 10 years.

Data monitoring

Since the study is labelled as low risk, a data safety monitoring board is not required.

References

- [1] M. Neubauer, "DASH Score," *Heartbeat Medical*, Jul. 22, 2021. <https://heartbeat-med.com/resources/dash-score/> (accessed Nov. 06, 2022).

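### Paid-work status is neither recorded at baseline nor used in the cost analysis, so the productivity-cost difference is less precise than it need be

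*Combined protocol and SAP*

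**What the plan says.** The section on cost-effectiveness analysis states: "Both cost-effectiveness (CEA) and cost-utility (CUA) analysis will be performed from a societal perspective". On lost work it adds: "Productivity costs will be registered in detail by the iPCQ". The same section plans ICERs, and 1000 bootstrap replications for 95% intervals around cost differences. It names no covariate for costs, and its sensitivity analysis mentions neither work status nor a result limited to health-care costs. Under the data analysis heading, covariates are named only for the re-displacement model.

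On baseline data, the section on study procedures says: "The list of baseline characteristics is shown in Table 2". Table 2 includes date of birth, sex, hand dominance, smoking and medical history, but no item on employment, occupation or working hours. In Table 1 the iPCQ row has three ticks, at T3, T4 and T5.

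On the sample, the abstract says: "In total, 30 patients will be included and followed for 6 months". The inclusion criteria admit patients from age 21 with no upper limit, and the Background says of the condition: "This is an issue which is pervasive across all ages, but most common in the elderly". On allocation, the design section says: "Randomisation will be carried out via block randomisation via a computer generated randomization sequence". It names no stratification factor.

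**The concern.** A patient without paid work has no absence from paid work to cost, while a worker may have a substantial amount. The eligible population can contain both kinds of patient in quantity. The cast cannot change who had a job before the injury, yet in a trial of this size the number of workers can differ noticeably between arms by chance. Neither the randomisation nor the described analysis balances or removes that difference.

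What is at stake is the precision and readability of the cost comparison. The Background argues that the new cast may save on cast changes and materials. Those are health-care costs. If they are read only as part of a societal total, chance variation in lost work is added to a comparison that it says nothing about.

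**Working it through.** **Inputs from the documents.** 30 patients, two groups, block randomisation without a named stratum, societal costs including the iPCQ. The documents give no employed share, cost mean, cost SD or allocation ratio, and no calculation behind the figure of 30, so there is no figure of the plan's own to reproduce.

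**Assumptions.** 15 patients per arm; proportion in paid work p from 0.3 to 0.7; mean productivity cost per worker M; coefficient of variation among workers (CV) from 0.5 to 1.5; productivity cost of zero for patients without paid work (the iPCQ items are not shown).

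**Step 1: how often the arms differ.** With X1 and X2 independent binomial(15, p), exact enumeration gives:

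| Gap in number of workers | p = 0.3 or 0.7 | p = 0.5 |
|---|---|---|
| 3 or more | 31.8% | 36.2% |
| 4 or more | 16.1% | 20.0% |
| 5 or more | 7.1% | 9.9% |

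The SD of the difference in proportion employed is sqrt(2p(1-p)/15): 0.167 at p = 0.3 or 0.7, and 0.183 at p = 0.5. Splits from 14:16 to 12:18 leave it at 0.183 to 0.186 (p = 0.5). If the number employed is instead fixed at 9 to 21 of 30, a gap of 3 or more has probability 26-47%.

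**Step 2: what a gap is worth.** A gap of 3 workers shifts the mean difference by 3/15 = 0.2M. A true cut of r in productivity cost per worker is worth p × r × M per patient. The probability that the imbalance term alone exceeds that effect, over p = 0.3 to 0.7, is:

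| True cut per worker | Probability |
|---|---|
| 10% | 55-86% |
| 20% | 32-84% |
| 30% | 16-55% |
| 50% | 3-32% |

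**Step 3: what adjustment gains.** In units of M, the variance of the productivity-cost difference is 2[p(1-p) + p·CV²]/15 unadjusted and 2[p·CV²]/15 with work status removed. The second is idealised: it ignores the small cost of estimating the covariate's coefficient.

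- p = 0.5, CV = 1: sqrt(2 × 0.75/15) = 0.316 falls to sqrt(2 × 0.50/15) = 0.258, a reduction of 18%. The variance ratio is 0.75/0.50 = 1.5, equivalent to 50% more patients for this component.
- p = 0.3, CV = 0.5 (largest gain): 0.195 falls to 0.100, 49%.
- p = 0.7, CV = 1.5 (smallest gain): 0.488 falls to 0.458, 6%.

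The share of variance due to work status is (1-p)/(CV² + 1-p): 33% in the central case, range 12-74%.

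**Step 4: what remains.** At p = 0.5 the 95% half-width after adjustment is still 0.25M to 0.76M, against 0.44M to 0.84M before.

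**The case against.** The strongest reply is that patients are randomised, so an imbalance in work status is ordinary sampling error that the bootstrap interval already contains. That is correct. The interval is valid, only wider than it need be. A 3-worker gap (0.2M) is about 0.63 of the unadjusted standard error in the central case (0.2/0.316), and two thirds of the variance there comes from differences among workers, which adjustment does not touch.

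A reader might infer that worker imbalance can swamp any cost effect, or that it drives the total and sets the sign of the ICER. The documents do not support this. A halving of productivity cost per worker would be exceeded in only 3-32% of trials, and cast and visit costs are not absence costs. All the arithmetic above concerns the productivity component. No cast, visit, surgery or productivity cost is given, so that component's weight in the total cannot be judged.

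A reader might also infer that the plan commits to an unadjusted difference reported only as a lump sum. It does not. The estimator is unstated, and the section derives cast application, intramural, medical and productivity costs separately. The gap is a lack of specification.

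Finally, work status before injury might be recovered from the later iPCQ, and date of birth is a partial proxy. If the answer refers to the time before injury, late collection does not invalidate it as a covariate. But the iPCQ items are not shown, and the secondary outcomes section ends trial procedures for patients who go to surgery after displacement at week 1 or 2. They may never complete an iPCQ, which is the main argument for asking at T0.

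**Conclusion.** The point stands as a minor one. Productivity costs enter the societal cost difference, paid work is not a listed baseline variable, and no cost covariate is described. The consequence is avoidable loss of precision in the productivity component, without bias. With 15 per arm and 30-70% employed, a gap of 3 or more workers would occur in about a third of trials, enough to exceed a small or moderate effect on productivity cost. Adjustment would reduce that component's standard error by about 18% in the central case and by 6-49% over the assumed range. The effect on total cost and the ICER is unknown. Adjustment would not make a 30-patient cost estimate precise. The employed share, the CV, equal arms and zero cost for patients without paid work are all assumptions.

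**What to change.** 1. Add pre-injury paid work (yes or no) and weekly hours to the existing T0 patient questionnaire and to Table 2, completed before allocation.
2. Pre-specify the cost difference as the arm coefficient from a regression of cost on arm and baseline paid-work status, refitted within each bootstrap replicate.
3. Report the health-care and productivity cost differences separately as well as in total, so that any saving on casts and cast changes can be seen.

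The cost is one or two questions, one degree of freedom and slightly more analysis work. The T0 items should be added before enrolment starts.
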